10. RANDOMIZATION AND BLINDING

10.1. Randomization

All subjects who are screened (including screen failures) will be assigned a unique subject identification number.

On Day 1, eligible subjects will be assigned another unique number (randomization number) in sequential order. The randomization number codes the subject's initial treatment assignment according to the randomization schedule generated prior to the study. Randomization will be stratified by use of HU and by region (regions will be defined in the statistical analysis plan). Initially, subjects will be randomly assigned in a 2:1 ratio to receive either IMR-687 lower dose or placebo. If the DMC recommends inclusion of the higher dose, randomization will then proceed in a 1:2:1 ratio (IMR-687 lower dose, IMR-687 higher dose, or placebo).

Randomization numbers will not be re-used once assigned. In the event that a subject is replaced (refer to Section 8.6), the replacement subject will receive the same treatment assignment as the replaced subject, and a different leading number will be used for the replacement randomization number. Additional details on randomization will be specified in the randomization plan provided by the interactive voice/web response system (IXRS) vendor.

10.2. Blinding

To ensure that the subject and site are blinded with respect to each subject's treatment assignment, placebo tablets and tablets for each dose level of IMR-687 are identical in appearance and are supplied in identical packaging. Each bottle will contain a code that identifies the contents as either 100 mg IMR-687, 150 mg IMR-687, 200 mg IMR-687, or placebo.

Every attempt should be made to preserve the integrity of study drug blinding. Except for cases of emergency unblinding, as described in Section 10.4, the randomization code will remain unbroken for subjects and study personnel at the site until the database has been locked. The blinded sponsor and contract research organization (CRO) study team members will be unblinded to the analysis results at the conclusion of the study (e.g., database lock).

10.3. Unblinding for Interim Analyses

To facilitate the IAs, certain sponsor representatives and designees will be unblinded to treatment assignments prior to and during the IAs (including the unblinded CRO biostatistician and external groups for bioanalytical, PK, and PK/PD analyses). Details will be provided in the study unblinding plan.

10.4. Emergency Unblinding

Unblinding is not always necessary to provide effective medical intervention and subject management in the event that a subject experiences a VOC, an SAE, or an event that results in cessation of treatment (see Section 8.7). However, in the exceptional circumstance in which the investigator believes that knowledge of the study drug assignment is essential to provide appropriate medical management, the treatment assignment for that subject will be provided to the investigator according to standard operating procedures at the CRO. The medical monitor and sponsor are available to the investigator as needed for any considerations of unblinding a

specific subject; however, the decision to unblind a specific subject relies solely on the clinical judgement of the investigator. That is, there is no requirement to discuss with the medical monitor and/or sponsor prior to unblinding a specific subject by the investigator; however, consultation is preferred. In the event that the investigator must unblind a subject and has not consulted with the medical monitor and/or sponsor, the investigator should notify the medical monitor and sponsor of the unblinding within 24 hours of breaking the blind.

After breaking the blind, the site staff should record the reason(s) for breaking the blind and any AEs leading to the breaking of the blind in the source documents and the appropriate eCRF pages. After breaking the blind, the subject will be discontinued from the study and should proceed with the ET and EOS visits according to the schedule of assessments ([Table 1](#)).

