13.5.2.3 Missing Value Consideration for the Primary Efficacy Analysis

The value of the primary endpoint, annualized rate of VOCs, will be non-missing by definition. However, subjects included in the ITT analysis may not all complete the 52-week treatment period. In the context of this endpoint, the unobserved VOC events after treatment discontinuation will be considered missing values. This calculation accounts for early treatment discontinuation by extrapolating the VOC rate annualized to one year. The primary analysis assumes the unobserved rate of VOC will be the same for the observed rate for the same subject.

Missing data will not be imputed for primary endpoint analysis methods. Data imputation strategies will be employed for sensitivity analysis.

Understanding the reasons why data are missing is important to correctly interpret and handle the observed data. If the missing data mechanism is independent of missing outcome values, conditional on earlier observed outcome variables and/or covariates, the outcome values are missing at random (MAR). If the probability of missingness depends on an outside variable not in the model or is related to unobserved outcome values at the time of dropout and possibly afterward then the values are missing not at random (MNAR).

Table 8 summarizes the classification with the potential reasons. The missing data pattern will be summarized and the impact of these missing values will be explored in the sensitivity analysis below.

Table 8 Classification of Missing Data Pattern

| Missing Data Pattern | Reason for Treatment Discontinuation |
|------------------------------|---|
| MNAR (Missing Not at Random) | 
Due to efficacy/safety related reasons:
 
 • Adverse Event • Death • Lack of Efficacy • Lost to Follow-up • Non-Compliance with Study Protocol • Non-Compliance with Study Drug • Physician Decision • Study Terminated by Sponsor • Subject Participation in Another Investigational Study • Trial Site Terminated by Sponsor • Withdrawal of Consent • Other (efficacy/safety related) |
| MAR (Missing at Random) | 
Due to non-efficacy/non-safety related reasons:
 
 • Pregnancy • Study Blind Intentionally or Accidentally Broken • Subject Erroneously Included in Study (i.e. did not meet eligibility criteria) • COVID-19 • Other (not efficacy/safety related) |

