4.2 Tipping Point Analysis #2 – MNAR with J2R

This tipping point analysis will be based on the J2R reference imputation, where the reference refers to the average annualized rate of VOCs among the completers in the placebo group in Section 4.1 Assuming the p-values for the primary comparison (highest tolerated dose vs placebo) are still significant with J2R (using prorogated alpha from IA), incremental changes (delta) in the referenced rate will be applied to the periods deemed to be MNAR, for the dropout subjects in the IMR-687 dose groups. If during the course of incrementing delta, the study conclusions change from favorable to unfavorable for the IMR-687 highest tolerated dose group, a tipping point is reached. The delta change will start from 0, and increment at a rate of 0.5 event/year, but granularity can be adjusted by incrementing by smaller or large amounts as needed.

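### SAP Table 8 treats a deliberate, medically driven code break as a non-safety dropout, so Tipping Point #2 never stresses those subjects beyond the placebo rate

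*Protocol*

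**What the plan says.** **Protocol.** Section 10.2: "Except for cases of emergency unblinding, as described in Section 10.4, the randomization code will remain unbroken" at the site until database lock. Section 10.4 sets the condition for an exception: in exceptional circumstances, when the "investigator believes that knowledge of the study drug assignment is essential to provide appropriate medical management". The site should then "record the reason(s) for breaking the blind and any AEs leading to the breaking of the blind" in the source documents and eCRF. The consequence is stated in the same section: "After breaking the blind, the subject will be discontinued from the study and should proceed with the ET and EOS visits". Section 8.4 lists deliberate and accidental breaks together as one justifiable reason for discontinuation.

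**SAP.** Table 8 (Section 13.5.2.3) sorts reasons for treatment discontinuation into MNAR and MAR. The entry "Study Blind Intentionally or Accidentally Broken" is in the MAR row, under the label "Due to non-efficacy/non-safety related reasons". Tipping Point Analysis #2 (Section 13.5.2.4, item 4.2) starts from the J2R imputation of item 4.1 and then raises the reference rate in steps of 0.5 event/year. These increments are "applied to the periods deemed to be MNAR, for the dropout subjects in the IMR-687 dose groups". Item 4.1 applies J2R to IMR-687 non-completers without regard to the reason for stopping.

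**The concern.** For deliberate breaks, the Table 8 label does not fit the protocol. A compliant break by a site is a medical decision about a particular patient, and discontinuation follows from it. Calling that dropout unrelated to efficacy or safety is hard to defend. It is also out of line with the rest of the table, where Lost to Follow-up, Physician Decision, and termination of the study or a site by the sponsor are all MNAR. A subject at a closed site is stress-tested; one withdrawn after an emergency code break is not.

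Tipping Point #2 is meant to show how poor the unobserved outcomes of IMR-687 dropouts would have to be to overturn a significant result. Delta is applied only in the IMR-687 arms. Withholding it from some of those dropouts can only push the tipping point further away, which favours the drug.

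**Working it through.** **1. The route through the documents.**
- Permitted site-level break before lock: only under Protocol 10.4, when essential for medical management.
- Consequence: discontinuation from the study.
- Class in SAP Table 8 if the coded reason is the broken blind: MAR.
- Treatment in item 4.1: J2R, so the remaining time takes the placebo-completer rate.
- Treatment in item 4.2: no delta, because the period is not MNAR.

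**2. What this does to one subject (illustration).** The placebo-completer rate is assumed to be 5.0/year, the SAP's power assumption for placebo. The subject values are also assumed. With N observed VOCs, R remaining days and T total days:

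rate = [N + (5.0 + delta) × R/365.25] / (T/365.25)

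The last dose is on Day 120. By the SAP's date rule, R = 364 − 119 + 1 = 246 and T = 120 + 246 = 366. With N = 1, the subject's own annualized rate is 1/(120/365.25) = 3.04. At delta 0 the rate is (1 + 5 × 246/365.25)/(366/365.25) = 4.36.

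| Delta (events/year) | 0 | 0.5 | 2 | 5 |
|---|---|---|---|---|
| Rate as classed now (MAR) | 4.36 | 4.36 | 4.36 | 4.36 |
| Rate if classed MNAR | 4.36 | 4.69 | 5.70 | 7.72 |

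J2R alone can work in either direction. With 1 VOC and a stop at Day 240, it raises the rate from 1.52 to 2.72. With 1 VOC and a stop at Day 60, it lowers the rate from 6.09 to 5.18. With 4 VOCs by Day 120, it lowers the rate from 12.18 to 7.35. For a subject doing worse than placebo before the break, J2R is a benefit, and delta is the only part of the analysis that goes beyond the placebo rate.

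The formula above is the evident intent of item 4.1. As printed, its brackets also divide the observed count by 365.25, giving (1 + 5 × 246)/365.25 = 3.37 instead of 4.36. That is a separate correction.

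**3. Effect on the test.** The plan has no figure for this point. As a check on the shared inputs, the SAP's power of 88.0% (31 and 49 subjects) recomputes to 88.6%, and 77.6% (24 and 37) to 78.8%.

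The simulation uses an unstratified Wilcoxon test with 31 placebo subjects from N(5, 2.7) and 49 active subjects with SD 2.7. Of the active subjects, k are unblinded at Week 13, so each takes 0.25 × own rate + 0.75 × 5, then + 0.75 × delta if MNAR. The table gives the share of J2R results significant at 0.0494 that become non-significant at delta 4 once the k subjects receive delta:

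| Active mean | k = 1 | k = 2 | k = 3 |
|---|---|---|---|
| 3.3 | about 5% | about 11% | about 19% |
| 3.0 (SAP assumption) | about 3% | about 7% | about 12% |

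The corresponding shifts in z are about 0.12, 0.23 and 0.35. Delta 4 means 9 VOCs/year after dropout. At delta 1 and mean 3.0, the shares are below 4% for all three k.

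These runs contain no other dropouts, so they do not measure the tipping point itself. With 12 active-arm dropouts in all (about 25% of 49), the others assumed to stop at mid-study, the median tipping point fell by about 0.5 events/year per reclassified subject.

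**The case against.** Several points on the other side stand.

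- **J2R already acts on these subjects.** A reader might infer that the tipping-point analysis ignores them altogether. It does not: item 4.1 moves them to the placebo-completer rate, and Tipping Point #1 shifts every subject's rate by −50% to +50% whatever the dropout reason. Only the delta increments are withheld.
- **The coded reason may be something else.** Adverse Event, Lack of Efficacy, Physician Decision and Other (efficacy/safety related) are all MNAR. A subject withdrawn for an SAE whose primary reason is coded Adverse Event already gets delta. The gap is confined to subjects whose coded reason is the broken blind. The SAP does not say which reason prevails when both apply.
- **Protocol 10.4 does not name VOCs or SAEs as the trigger.** A reader might infer that it does, but the sentence mentioning them says unblinding is not always necessary for such events. The trigger is the investigator's judgement about medical management. Sites record any AEs that led to the break, and there may be none.
- **MAR is arguable.** The SAP defines it as missingness independent of the unobserved outcome given what was observed, and a rule-driven withdrawal after an observed event could meet that. But Table 8 sorts by whether the reason is related to efficacy or safety, and on that criterion the present label is not justified for deliberate breaks.
- **The consequence is limited.** Tipping Point #2 runs only if the J2R comparison is significant. The primary test, the alpha and the success criterion do not depend on Table 8.

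**Conclusion.** The concern holds in a narrow form. For deliberate breaks, the Table 8 label conflicts with Protocol 10.2 and 10.4. IMR-687 subjects carrying that code are held at the J2R value at every delta, so their post-dropout rate is never stressed beyond the placebo rate. Any resulting error favours the drug.

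The size is probably small and cannot be computed for this trial, because the number of emergency unblindings is not given. With none, there is no effect. With one to three, the simulation suggests roughly one grid step of 0.5 event/year per subject. That figure rests on the assumed placebo rate, Week 13 stopping time, normal rates, unstratified test and 12 active dropouts. A reader might infer that the primary efficacy conclusion is at risk; the documents do not support that, since only this sensitivity analysis is affected. This is a minor correction, worth making because it is nearly free.

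**What to change.** In SAP Table 8, split the row in two:

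1. Study blind intentionally broken under Protocol 10.4: MNAR, unless the recorded reason is clearly unrelated to efficacy or safety.
2. Study blind accidentally broken: MAR, unless the recorded reason or a linked AE is efficacy- or safety-related.

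Add one sentence stating that an underlying AE or efficacy reason takes precedence over the broken-blind code when the missing-data class is assigned. Make the assignments blinded to treatment arm where possible, and fix the rule before the interim unblinding.

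No new data are needed, because Protocol 10.4 already asks sites to record the reason for the break and any AEs behind it. The cost is a small edit to one table and a tipping point that may be slightly less favourable to the drug.

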11. ASSESSMENTS

Refer to the schedule of assessments ([Table 1](#)) for the timing of the assessments described below. All data obtained from these assessments must be documented in the subject's source documentation.

Subjects should be seen for all visits on the designated day or within the defined allowable visit window ([Table 1](#)). The visits are as follows:

- Screening (up to 28 days prior to Baseline)
- Baseline (Day 1)
- Treatment Period (Week 1 to Week 52)
 - Telephone visits will be performed at Week 2 and Week 6
- EOT/ET (Week 52)
- EOS (Week 56)

Unless otherwise specified, all assessments should be completed prior to dosing at any given timepoint.

11.1. Screening and Baseline Activities

The descriptions below are for screening-specific activities. For descriptions of activities that occur during both the screening and treatment periods, refer to Section [11.2](#) for PD/efficacy assessments, Section [11.3](#) for safety assessments, and Section [11.4](#) for PK assessments.

11.1.1. Informed Consent

The subject must read, understand, and sign the IRB/IEC-approved ICF confirming his or her willingness to participate in this study before initiating any screening activity that is not standard of care. The investigator will ensure that the subject has received adequate language translation if needed and understands the ICF before signing as per the local IRB/IEC's requirement. Subjects must also grant permission or be informed of national laws for the processing and dissemination of their personal data, including data concerning health (sensitive/protected health information) and the use and retention of their specimens for study-related purposes.

11.1.2. Demographic Information and Medical/Disease History

Subject demographics (age, sex, race, and ethnicity) and medical disease history (by thorough review of medical records and by interview) will be recorded at screening, in accordance with country requirements and institutional policies, and captured in the eCRF. Concurrent medical signs and symptoms must be documented to establish baseline severities.

The diagnosis of SCD (HbSS, HbS β^0 thalassemia, or HbS β^+ thalassemia) should be confirmed in the medical record; if not available, the diagnosis must be confirmed at the site's local laboratory instead.

11.1.3. Inclusion/Exclusion Criteria Evaluation

Eligibility will be assessed based on the inclusion and exclusion criteria provided in Section 8. All inclusion and exclusion criteria will be assessed at the screening visit; continued eligibility based on these criteria will be confirmed on Day 1.

11.1.4. Height

Height in centimeters (cm) will be measured at the screening and EOT/ET visits ([Table 1](#)).

11.1.5. Serum Virology

Blood samples will be collected for serum virology (screening assessment) only if clinically indicated. Testing will be performed through a central laboratory and may include hepatitis B surface antigen (HBsAg), hepatitis A immunoglobulin M (IgM), and hepatitis C virus (HCV) antibody, as well as HIV testing.

11.2. Efficacy and Pharmacodynamic Assessments

11.2.1. Specialty Hematology

Blood samples will be collected for HbF and % F-cells at selected study visits as shown in the schedule of assessments ([Table 1](#)). Refer to the specialty laboratory manual for details on the collection, handling, and processing of blood samples.

11.2.2. Pharmacodynamic Assessments

Blood samples will be collected for the following efficacy/PD laboratory assessments, many of which are routine clinical safety laboratory assessments, at selected study visits as shown in the schedule of assessments ([Table 1](#)).

- Biomarkers of RBC hemolysis (% and absolute reticulocytes, unconjugated [indirect] bilirubin, and LDH)
- Biomarkers of adhesion: soluble E-sel, P-sel, ICAM-1, and VCAM-1
- Biomarkers of inflammation: hsCRP and MPO
- Biomarker of cardiac stress: NT-proBNP
- RBC indices (e.g., MCV) and total Hb

Refer to Section [11.3.6](#) for additional details on clinical laboratory assessments.

Refer to the central laboratory manual for details on the collection, handling, and processing of blood samples.

11.2.3. Clinical Assessment: VOCs

VOC is defined as a documented episode of an acute painful crisis (for which there was not an explanation other than VOC) that involves moderate to severe pain lasting for at least 2 hours and at least one of the following:

- Use of escalated analgesia (including healthcare professional-instructed use of an analgesic prescription)
- A hospital, emergency department, or clinic visit and/or healthcare telephone consultation at the time of occurrence
- Diagnosis of ACS (defined as an acute illness characterized by fever and/or respiratory symptoms, accompanied by a new pulmonary infiltrate on a chest X-ray), hepatic sequestration, splenic sequestration, or priapism (in males)

11.2.4. Quality of Life Assessments

Data on QoL will be collected as per the schedule of assessments ([Table 1](#)).

The Adult Sickle Cell Quality of Life Measurement Information System (ASCQ-Me[®]) is a systematic, reliable, and valid method for documenting adult SCD patient-reported outcomes. The questions are grouped into 3 domains (physical, social, and emotional) encompassing 7 subdomains, of which the following 5 will be measured: emotional impact, pain impact, sleep impact, social functioning impact, and stiffness impact. (Note: pain episodes and frequency, and SCD medical history checklist will not be evaluated). Each subdomain includes 5 to 9 items. Recall periods vary by subdomain and even question, with most of the periods being from 7 days to 30 days ([Keller 2014](#)).

The Patient-Reported Outcomes Measurement Information System (PROMIS[®]), is a National Institutes of Health initiative to develop state-of-the-science self-report measures to assess functioning and well-being in physical, mental, and social domains of health. The PROMIS - Preference (PROMIS[®] 29 + 2 Profile v 2.1 [PROPr]) score can be estimated using the following 7 PROMIS domains: cognitive function, emotional distress, fatigue, pain interference, physical function, ability to participate in social roles and activities, and sleep disturbance. Each domain is rated on a 5-point Likert scale. Recall periods vary by subdomain with most periods being in the past 7 days ([Hanmer 2018](#)). The translated QoL assessments from PROPr will be used when available.

The Sickle Cell Self-Efficacy Scale (SCSES) is a 9-item QoL measure for adults with SCD. This measure is a self-appraisal of an SCD patient's ability to engage in daily functional activities and to manage SCD symptomatology. Response choices range from "not at all sure" to "very sure" ([Edwards 2000](#)).

11.3. Safety Assessments

11.3.1. Telephone Visits

Qualified site personnel will contact the subject by telephone at Week 2 and Week 6 to capture potential TEAEs and concomitant medications. Subjects will also be reminded of compliance with study drug and the next visit schedule. If any AEs of significant clinical concern are

identified during the telephonic visit, the subject will be requested to come into the site to be assessed.

11.3.2. Vital Signs

Vital signs include heart rate, respiratory rate, blood pressure, and body temperature and should be consistently measured in either the sitting or semi-supine position. Vital signs will be collected at every on-site visit (Table 1). At the Day 1 and Week 4 visits, vital signs will be taken pre-dose and 2 hours (± 20 minutes) post-dose, during the PK assessments. At all other timepoints, vital signs can be taken irrespective of taking study drug. Vital signs that are clinically significant and not explained by the underlying disease or concomitant medications should be recorded as AEs in the eCRF.

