12. SAFETY MONITORING AND REPORTING

12.1.1. Adverse Event and Serious Adverse Event Collection

12.1.1.1. Time Period Adverse Event Collection

All AEs and SAEs, related and unrelated, will be recorded from the signing of informed consent through the EOS safety follow-up visit. Events that occur following administration of study drug will be considered TEAEs.

All SAEs will be recorded and reported to the sponsor or sponsor's designee within 24 hours, as indicated in Section 12.1.2.3. The investigator will also submit any updated SAE data to the sponsor within 24 hours of the data being available.

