12.1.2. Adverse Event Recording and Reporting

12.1.2.1. Definitions

12.1.2.1.1. Definition of an Adverse Event

An AE is defined as any untoward medical occurrence in a clinical study subject administered a pharmaceutical product and which does not necessarily have a causal relationship with this treatment. An AE can therefore be any unfavorable or unintended sign (for example, an abnormal laboratory finding), symptom, or disease temporally associated with the use of a medicinal (investigational) product, whether or not considered related to the medicinal (investigational) product.

Examples of AEs include, but are not limited to, the following:

- Abnormal test findings
- Clinically significant symptoms and signs
- Changes in PE findings
- Hypersensitivity
- Drug abuse
- Drug dependency

Additionally, AEs may include the signs or symptoms resulting from:

- Drug overdose
- Drug withdrawal
- Drug misuse

- Drug interactions
- Extravasation
- Exposure during pregnancy
- Exposure via breastfeeding
- Medication error

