12.1.2.2.2. Assessment of Causality

The investigator will assess the potential relatedness of each AE to the investigational product. An investigator causality assessment (unlikely/not related, possible, probable/likely, or certain/related) must be provided for all AEs (both serious and non-serious). This assessment must be recorded on the eCRF and any additional forms as appropriate.

- Unlikely/Not Related:**
 - Event or laboratory test abnormality, with a time to drug intake that makes a relationship improbable (but not impossible)
 - Disease or other drugs provide plausible explanations
- Possible:**
 - Event or laboratory test abnormality, with reasonable time relationship to drug intake
 - Could also be explained by disease or other drugs
 - Information on drug withdrawal may be lacking or unclear

Probable/Likely:

- Event or laboratory test abnormality, with reasonable time relationship to drug intake
- Unlikely to be attributed to disease or other drugs
- Response to withdrawal clinically reasonable
- Rechallenge not required

Certain/Related:

- Event or laboratory test abnormality, with plausible time relationship to drug intake
- Cannot be explained by disease or other drugs
- Response to withdrawal plausible (pharmacologically, pathologically)
- Event definitive pharmacologically or phenomenologically (i.e., an objective and specific medical disorder or a recognized pharmacological phenomenon)
- Rechallenge satisfactory, if necessary

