9.2 Safety Endpoints

Safety endpoints include the number and percentage of subjects with the following:

- At least one treatment-emergent adverse events (AEs)
- At least one treatment-emergent serious adverse events (SAEs)
- At least one clinically significant change in a laboratory test parameter
- At least one clinically significant change in a vital signs parameter
- At least one clinically significant change in an electrocardiogram (ECG) parameter

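### Protocol 11.3.2 makes the absence of another explanation a condition for recording a clinically significant vital-sign finding as an AE, which conflicts with the all-AE rule and can under-record vital-sign AEs

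*Protocol*

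**What the plan says.** Protocol 11.3.2 (Vital Signs) has vital signs collected at every on-site visit and says that those that are "clinically significant and not explained by the underlying disease or concomitant medications should be recorded as AEs".

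Protocol section 12 sets the general rule. Section 12.1.1.1 states: "All AEs and SAEs, related and unrelated, will be recorded from the signing of informed consent through the EOS safety follow-up visit". Section 12.1.2.1.1 defines an AE as an untoward occurrence "which does not necessarily have a causal relationship with this treatment", and extends this to any unfavourable sign "whether or not considered related to the medicinal (investigational) product". Section 12.1.2.3 requires all AEs, serious or not, to go into the eCRF.

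Causality is a separate, later step. In section 12.1.2.2.2, one feature of the Possible category is: "Could also be explained by disease or other drugs". SAP 13.5.8.1 counts a TEAE graded Possible or higher as treatment-related.

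For vital signs as data, SAP 13.5.8.3 summarises five parameters by visit and arm and counts outliers against Table 10. SAP 9.2 also lists a safety endpoint: "At least one clinically significant change in a vital signs parameter".

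**The concern.** Section 11.3.2 asks the investigator to decide whether sickle cell disease or another medicine accounts for a finding before deciding whether it is an AE at all. That is the question the causality scale exists to answer, and the scale answers it for events already in the database.

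The order matters because the AE outputs start from what was recorded. An event left out at this point cannot appear in the TEAE, Grade 3 or higher or treatment-related tables of SAP 13.5.8.1, nor in AE summaries supplied to the DMC.

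Heart rate is a parameter the protocol itself watches. Section 5.2.2.3 describes heart-rate increases in dogs and sporadic tachycardia in volunteers, and asks that pain and dehydration be considered as other causes. Competing explanations are therefore foreseeable in this population.

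**Working it through.** No figure in the documents bears on this point, so the check sets the rules side by side.

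**What triggers an AE record**

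| Protocol section | Clinically significant finding is an AE if | Exempt if otherwise explained? |
|---|---|---|
| 11.3.2 Vital signs | not accounted for by disease or other medication | Yes, by implication |
| 11.3.4 Physical examination | new or worse after consent and within the AE definition | No |
| 11.3.5 ECG | new or worse after consent | No |
| 11.3.6 Laboratory | found after screening | No |
| 12.1.1.1, 12.1.2.1.1, 12.1.2.3 | any AE | No |

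Vital signs are the only assessment with the extra condition.

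**What happens to one event under each rule.** Take a clinically significant vital-sign change that the investigator thinks disease or another drug explains.

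1. Under 11.3.2 it need not be recorded.
2. Under section 12 it is recorded and graded. Depending on how firm the alternative explanation is, the grade is Unlikely/Not Related (disease or other drugs plausible) or Possible (they could also explain it).
3. With either grade it counts in the TEAE tables. If graded Possible, it also counts as treatment-related under SAP 13.5.8.1.

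Section 11.3.2 does not say how firm the explanation must be, so its exemption can reach events of both grades.

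**The two parts of the exemption**

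- *Underlying disease.* If the explanation is a crisis, the crisis has its own CRF page (SAP 13.5.2.1) and can be an AE, since SAP 13.5.4 identifies hospitalisations from AEs coded to that term. Part of the information is kept.
- *Concomitant medication.* Nothing comparable applies. Section 12.1.2.1.1 lists drug interactions among the sources of signs and symptoms that may be AEs. Section 5.2.3 says competition for CYP3A4 may raise exposure to IMR-687, to the other drug, or to both. A change put down to another medicine may therefore be an interaction effect, which section 12 treats as a possible AE and 11.3.2 exempts.

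**What survives outside the AE form.** Of the five vital signs summarised in SAP 13.5.8.3, three (heart rate, SBP, DBP) have Table 10 criteria, applied to every post-baseline value including unscheduled visits, with no reference to cause. For heart rate these include at least 100 bpm and at least 120 bpm, each with a rise of at least 15 bpm. The other two (temperature and respiratory rate) have descriptive summaries only, so AE records are their only specified categorical output.

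**Direction of any effect.** Let the true proportions with a vital-sign AE be pD (drug) and pP (placebo), and the fractions left unrecorded fD and fP.

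- Recorded risk ratio = (pD/pP) × (1 − fD)/(1 − fP).
- If fD = fP = f, the ratio is unchanged and the difference becomes (1 − f)(pD − pP), which is smaller in size.
- If fD > fP, because drug effects are mistaken for disease, the recorded ratio falls.
- If fP > fD, because mainly disease-driven background events are dropped, the recorded ratio rises.

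The documents give none of the four quantities.

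**The case against.** The strongest reply is that this is a loosely worded sentence with ample backup. Several stronger readings are tempting, and the documents do not support them.

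- *That 11.3.2 forbids recording.* It is a positive instruction about what should be recorded, and the exclusion is only implied. Section 12 still binds sites. What stands is that they have two instructions that disagree.
- *That tachycardia would be hidden.* Heart rate is a named ECG parameter. ECGs are scheduled at the same visits as vital signs in Table 1 of the protocol, and clinically significant ECG findings that are new or worse must be recorded as AEs without exception. Table 10 and a heart-rate shift plot ignore attribution, all values are listed, and the DMC may review unblinded vital signs. This reply holds for heart rate at scheduled visits. It does not reach temperature or respiratory rate.
- *That the vital-sign endpoint in SAP 9.2 is filtered by attribution.* It is listed separately from the AE endpoint, and no section derives it from AE forms.
- *That the bias runs towards no difference.* Attribution is made blinded, and the algebra above shows that the relative contrast could stay the same, fall or rise.
- *That another explanation is nearly always to hand.* Section 5.2.2.3 says only that other causes should be considered when tachycardia is persistent or clinically significant.

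It is also fair to say that part of the exemption has a sensible purpose, namely avoiding a second AE for a sign of a crisis already reported. That can be achieved by recording under the diagnosis, as 11.3.6 does for laboratory results. It does not justify exempting findings put down to other medication.

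**Conclusion.** The point holds as a contradiction in the recording rules. Section 11.3.2 places a causality judgement ahead of the causality step, against section 12 and against the ECG and laboratory sections. If sites follow it, vital-sign AEs can be missing from the TEAE, Grade 3 or higher and treatment-related tables. The gap is widest for findings put down to concomitant medication, and for temperature and respiratory rate.

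The loss concerns AE records, not measurements. Its size cannot be estimated, because no vital-sign AE rate or attribution rate is given, and no direction of bias can be claimed. The conclusion assumes that at least some sites read 11.3.2 as the operative rule for vital signs. If all sites apply section 12 instead, nothing is lost and only the wording is wrong. The correction is worth making because it is cheap and the sentence is wrong as it stands.

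**What to change.** In Protocol 11.3.2, delete the condition about disease or concomitant medication. State instead that any clinically significant vital-sign finding that appears or worsens after consent is recorded as an AE, or under the diagnosis when it is part of an AE already recorded, and that alternative explanations are weighed in the causality assessment of 12.1.2.2.2. The first part brings the section into line with 11.3.5. The diagnosis provision is an addition that prevents double recording of crises.

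Send sites a short reminder. Because the values are retained, sites can also be asked, while still blinded, about past clinically significant findings that have no matching AE entry.

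The cost is one sentence, the reminder and slightly more AE records. No assessment is added.
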